3.9.3 Vital Signs

Descriptive statistics for vital signs (weight, temperature, blood pressure, pulse rate, and respiratory rate) values and the change from baseline will be presented for each scheduled assessment time point.

3.9.4 ECG

Descriptive statistics for ECG parameters (i.e., PR interval, QRS interval, and QTcF interval) at each time point with triplicate ECGs will be presented for the values and change from baseline scores (note: Fridericia's correction: $QTcF = QT/RR^{1/3}$).

The number and percentage of subjects with observed QTcF values that satisfy the following conditions will be presented by treatment group and study visit:

- ≤ 450 ms
- $>450 - 480$ ms
- $>480 - 500$ ms

- > 500 ms

The number and percentage of subjects having change from baseline QTcF values that satisfy the following conditions will be presented by treatment group and study visit:

- ≤ 0 ms
- >0 to ≤ 30 ms
- >30 to ≤ 60 ms
- > 60 ms

3.10 Pharmacokinetic Analysis

No pharmacokinetic analysis will be conducted.

3.11 Pharmacodynamic Analysis

Pharmacodynamics endpoints are included in exploratory analysis (section 3.8.3).

3.12 Sample Size Justification

A sample size of 36 subjects per cohort receiving KD025 will provide approximately 90% probability of 1 or more subjects in the cohort experiencing an AE that has an underlying rate of $\geq 6\%$ and approximately an 80% probability of 1 or more subjects in the cohort experiencing an AE that has an underlying rate of $\geq 4\%$.

An evaluable sample size of 30 subjects per cohort will provide approximately 85% power to detect a difference in the number of subjects that reach PASI 75 rates at Week 16 between a KD025 group and placebo, assuming rates of 33% and 5%, respectively, at a 5% 2-sided significance level using Fisher's Exact test. This assumes an observed case analysis with approximately 17% of subjects not having a Week 16 PASI score.

But due to newly available plaque psoriasis treatment, this study was terminated early with 110 subjects.

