### **12.2 Sample Size Justification**

The sample size will be 110 subjects due to early study termination.

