2.2 Study Design

This is a Phase 2, double blind, randomized, placebo-controlled, dose-finding, safety, tolerability, and efficacy study.

This study will be performed in adult male and female subjects with moderate to severe chronic plaque psoriasis who are candidates for systemic therapy or phototherapy. Subjects who have signed an Institutional Review Boards/Independent Ethics Committees (IRBs/IECs) approved informed consent form (ICF) and have met all of the inclusion/exclusion criteria will be enrolled. Approximately 110 subjects will be randomly assigned to each of the 5 dose cohorts in a 1:1:1:1:1 manner to achieve 22 evaluable subjects at 16 weeks in each cohort.

Table 1: Cohorts

Cohort	Number of Subjects	Treatment
Cohort 1	~22	200 mg KD025 QD
Cohort 2	~22	200 mg KD025 BID
Cohort 3	~22	400 mg KD025 QD
Cohort 4	~22	600 mg/day KD025 (administered as 400 mg in the morning and 200 mg in the evening)
Cohort 5	~22	Matching placebo BID

Study drug will be orally administered in a double-blind fashion for an initial 16 weeks. All subjects will be given the option to receive KD025 400 mg QD for an additional 32-weeks in an open-label treatment period (week 16 through week 48).

For all subjects, including those who discontinue from the study prematurely, a Follow-Up visit will occur 30 days (\pm 3 days) after the last dose of study drug.

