3.8 Efficacy Analysis

3.8.1 Primary Endpoint

- The number (%) of subjects with a 75% decrease in PASI by Week 16
In addition to the descriptive statistics (n, %, CI) for each group, the difference of the percentage of subjects with a 75% decrease in PASI by Week 16 between each treatment and control group will be analyzed with Fisher's exact method.

Patients without Week 16 assessment will be counted as failed to reach 75% decrease.

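### SAP 3.12 states about 85% power at 30 evaluable per cohort, but Fisher's exact test gives about 73%, and power at the 22 or so per cohort reached (about 60% at best) is not stated

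*SAP*

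**What the plan says.** SAP Section 3.12 holds the only power figure in either document: "An evaluable sample size of 30 subjects per cohort will provide approximately 85% power", "assuming rates of 33% and 5%, respectively, at a 5% 2-sided significance level using" Fisher's exact test. The 30 evaluable come from 36 enrolled per cohort: "This assumes an observed case analysis with approximately 17% of subjects not having a Week 16 PASI score".

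The section then closes by saying that "this study was terminated early with 110 subjects". Protocol Section 12.2 consists of one sentence, "The sample size will be 110 subjects due to early study termination", with no power. SAP Section 2.2 ("Approximately 110 subjects will be randomly assigned to each of the 5 dose cohorts in a 1:1:1:1:1 manner") and its cohort table put the final size at about 22 per cohort.

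The planned primary analysis in SAP Section 3.8.1 is Fisher's exact test of each KD025 cohort against placebo. Its missing-data rule is "Patients without Week 16 assessment will be counted as failed to reach 75% decrease". Protocol Section 12.7 makes no multiplicity adjustment, so each comparison is tested at 5%.

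**The concern.** Every input needed to check the power statement is printed beside it, and the result does not match. Fisher's exact test is conservative when one rate is near 5%, and approximate formulas tend to overstate its power at these sizes.

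The section also describes a size the trial did not reach. It sets the original calculation next to the early stop and leaves 85% as the only number. A reader who carries that forward would put the chance of missing a true 33% response rate at about 15% per dose. The actual chance at 22 per cohort is about 40% with complete data and about 53% under the plan's own missing-data assumption. In a dose-finding study, the risk is that a dose is set aside on a non-significant result that the trial was too small to interpret that way.

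**Working it through.** **Inputs.** Rates 0.33 and 0.05, two-sided 5% level, Fisher's exact test, 30 evaluable per cohort, 17% missing (SAP Section 3.12). Equal allocation and 110 / 5 = 22 per cohort (SAP Section 2.2). Missing Week 16 counts as failure (SAP Section 3.8.1).

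**Method.** Power = Σ P(X = a) · P(Y = b) over all pairs (a, b) with two-sided Fisher p ≤ 0.05, where X ~ Binomial(n, 0.33) and Y ~ Binomial(n, 0.05).

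**The plan's own figure, n = 30.** For each placebo count, find the smallest significant KD025 count and the chance of reaching it:

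| Placebo responders | Probability | KD025 responders needed | Chance at 33% | Product |
|---|---|---|---|---|
| 0 | 0.2146 | 6 | 0.9615 | 0.2064 |
| 1 | 0.3389 | 8 | 0.8235 | 0.2791 |
| 2 | 0.2586 | 9 | 0.7007 | 0.1812 |
| 3 | 0.1270 | 11 | 0.4000 | 0.0508 |
| 4 | 0.0451 | 12 | 0.2631 | 0.0119 |
| 5 or more | | | | 0.0020 |
| Total | | | | **0.7314** |

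Power is 73.1%, not about 85%. A simulation of 200,000 trials gives 73.15%.

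**Can another reading reach 85%?**
- Rounded rate: 1/3 in place of 0.33 gives 74.1%.
- Uneven arms: over all 25 combinations of 28 to 32 per arm, power runs from 68.1% to 83.5%.
- Enrolled instead of evaluable: Fisher at 36 per cohort gives 84.2%, but the sentence says 30 evaluable.
- Missing counted as failure at 36 enrolled: rates become 0.33 × 0.83 = 0.274 and 0.05 × 0.83 = 0.0415, and power is 72.1%.
- A different method at n = 30: the arcsine formula gives h = 2·asin√0.33 − 2·asin√0.05 = 0.773 and Φ(0.773·√15 − 1.96) = 84.9%. The uncorrected chi-square test gives 84.5% and the unpooled normal approximation 84.1%. None of these is Fisher's test.

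With equal arms, Fisher's power is 84.2% at 36 and 85.5% at 37, so 37 is the first size that reaches 85%.

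**Power at the size reached.**

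| Case, 33% vs 5% | Power |
|---|---|
| 22 per cohort, complete data | 59.5% |
| Any arm sizes from 20 to 24, complete data | 53.3% to 73.1% |
| 22 per cohort, 17% missing = failure (27.4% vs 4.15%) | 47.2% |
| 22 per cohort, 10% to 25% missing = failure | 52.5% to 40.7% |
| Observed case, 18 vs 18 (22 × 0.83 = 18.3) | 46.4% |
| Observed case, averaged over random numbers of completers | 52.3% |

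The missing-data rows assume the same missing rate in both arms, independent of response. The 17% is the plan's assumption for the larger design, carried over.

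**What a non-significant dose would mean at 22 per cohort.** Against 1/22 on placebo, 7/22 is significant (p = 0.046) and 6/22 is not (p = 0.095). Exact 95% intervals for the dose are:

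| Responders of 22 | 95% CI | Includes 33%? |
|---|---|---|
| 0 | 0 to 15.4% | no |
| 1 | 0.1% to 22.8% | no |
| 2 | 1.1% to 29.2% | no |
| 3 | 2.9% to 34.9% | yes |
| 6 | 10.7% to 50.2% | yes |

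If the true rate is 33%, a dose lands at 3 to 6 of 22 with probability 36.4%. With 1/22 on placebo, every such result is non-significant and still compatible with 33%. Letting the placebo count vary as well, the non-significant results split into 27.6% at 3 to 6 responders, 11.9% at 7 or more, and 1.0% at 0 to 2. These sum to 40.5% = 100% − 59.5%.

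**The case against.** The best counter-argument is that the 85% no longer drives anything. It describes the original design, the stop had an external cause, enrolment is closed, there is no interim analysis, and the protocol makes no power claim. The plan already calls the study exploratory and promises intervals ("In addition to the descriptive statistics (n, %, CI) for each group" in SAP Section 3.8.1; exact 95% intervals in Protocol Section 12.1). Nowhere does it say that a non-significant dose has no effect. This stands as a limit on the consequences: no analysis changes. It does not make the figure right, and the SAP chose to keep that figure beside the termination sentence.

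The illustration can also be pressed. One placebo responder of 22 has only a 37% chance at a 5% rate. With 0/22 (32%), 5/22 is enough (p = 0.048); with 2/22 (21%), 9/22 is needed. So 36.4% is the chance of an ambiguous negative given 1/22 on placebo, not overall. Likewise, the comparison with 33% is a complete-data reading. With 17% missing counted as failures, a true 33% appears as 27.4%, which the upper limit of 29.2% at 2/22 does not exclude. Both points qualify the example and leave the power figures as they are.

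Finally, the slip may lie in the method or the sample size rather than in the stated power; the documents do not say. But the sentence names Fisher's test and 30 evaluable, and for those inputs the answer is about 73%.

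**Conclusion.** The concern holds. The stated power is about 12 points too high for its own inputs: 73.1% against approximately 85%. The omission is also real, since neither document gives power at about 22 per cohort. That power is 59.5% as a best case, and about 47% if the plan's 17% missing rate applies and its missing-equals-failure rule is used. The figures rest on true rates of 33% and 5% and on equal cohorts of 22. The lower one also assumes that missingness is equal across arms and unrelated to response. This should be fixed because it is the only power statement for the primary comparison, but it concerns interpretation and the written record only. Fisher's test, the estimates and the number of subjects stay as they are.

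**What to change.** In SAP Section 3.12, change the stated power at 30 evaluable per cohort from approximately 85% to approximately 73%. If the sponsor wants to preserve the record of how the study was sized, a dated recalculation note beside the sentence would do the same job.

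After the sentence on early termination, add text such as:

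> With about 22 subjects per cohort, power for 33% vs 5% is about 60% with complete data and lower with missing Week 16 data (about 47% if 17% are missing and counted as failures, as in Section 3.8.1). A non-significant pairwise result should be read with its confidence interval and not taken alone as evidence of no effect.

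If the final cohort sizes differ from 22, compute the figure at the actual sizes. The intervals needed are already planned.

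Optional and minor: the same section's probability of seeing at least one adverse event with a 4% rate among 36 subjects is 1 − 0.96^36 = 77%, stated as about 80%.

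The cost is two wording changes in one SAP section. No protocol text, test, analysis or sample size changes. The only downside is a less favourable stated power.

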3.13 Interim Analysis

There is no interim analysis.

3.14 Primary CSR Analysis

A primary CSR analysis will be conducted after conclusion of the study.

4 List of Tables, Figures and Listings

In all tables, figures and listing, results will be presented by treatment cohorts and overall, unless be otherwise specified.

Table 2: Demographics and Baseline Characteristics TLFs

T/F/L	Title	Population
T	Subject disposition	mITT
L	Subject disposition	mITT
L	Protocol deviations	mITT
T	Demographics and baseline characteristics	mITT
L	Demographics and baseline characteristics	mITT
T	Medical histories by primary system organ class and preferred terms	mITT
L	Medical history	mITT

Table 3: Efficacy TLFs

T/F/L	Title	Population
PASI		
T	The number (%) of subjects with a 75% decrease in PASI by Week 16	mITT
T	The number (%) of subjects with a 75% decrease in PASI by Week 48	mITT
T	PASI score, change and % change from baseline by visit	mITT
T	PASI change and % change from Week 16 to Week 48 visit	mITT
PGA		
T	The number (%) of subjects with “clear” and “almost clear” (excellent) in PGA at Week 16, 48	mITT
DLQI		

T/F/L	Title	Population
T	DLQI score, change and % change from baseline by visit	mITT
Exploratory Endpoints		
T	Descriptive statistics for IL-17 by visit	mITT

Table 4: Safety TLFs

T/F/L	Title	Population
T	Concomitant medications	mITT
L	Concomitant medications	mITT
T	Treatment exposure and compliance	mITT
L	Treatment exposure and compliance	mITT
T	Dose modifications and interruption	mITT
L	Dose modifications and interruption	mITT
T	Overall summary of TEAEs	Safety
T	TEAEs by Soc/PT	Safety
T	TEAEs by PT	Safety
T	TEAEs by severity and PT	Safety
T	Treatment related AEs by PT	Safety
T	Serious TEAEs by Soc/PT	Safety
T	Serious TEAEs by PT	Safety
T	Treatment related SAEs by PT	Safety
T	Grade 3-5 TEAEs by Soc/PT	Safety
T	Grade 3-5 TEAEs by PT	Safety
T	Treatment related grade 3-5 AEs by Soc/PT	Safety
L	AEs	Safety
L	AE Leading to treatment discontinuation	Safety
L	Death	Safety
T	Lab values and their change from baseline	Safety
F	Lab values by visit	Safety
T	Shifts in CTC grade from baseline to highest grade post-baseline of laboratory	Safety
L	Lab values with CTC grade ≥ 3	Safety

T	Vital signs and their change from baseline	Safety
L	Vital signs	Safety
T	ECG parameters and their change from baseline	Safety
F	ECG parameters by visit	Safety
T	Number and percentage of subjects with QTcF by visit a) absolute ranges and b) change from baseline	Safety
T	QTcF abnormalities	Safety
L	ECG values	Safety
